### 8.2.12 Subgroup Analyses and Effect of Baseline Factors

Subgroup analyses will be conducted on CDR-SB, CCS-3D, ADCS-ADLMCI at Week 130. The consistency of treatment effect across various subgroups will be assessed through the computation of within group summary statistics (model-based and as-observed), along with nominal 95% CIs. Further, model-based between-group treatment differences (or hazard ratios, as appropriate) and the corresponding 95% CIs will be constructed for those comparisons (active/active vs. placebo/active), for which both treatment groups within the subgroup level have at least 75 subjects (roughly 15% of subjects randomized). No formal statistical testing of the treatment by subgroup interactions will be performed. The following subgroups will be examined:

- Gender (Male, Female);
- Age (< 65, ≥ 65 years of age);
- Race (white, black, Asian, other);
- Ethnicity (Hispanic, Not Hispanic);

- Geographic Region (US/Canada, Europe/Australia/New Zealand, Japan, Rest of World);
- APOE Genotype (APOE 4 positive, APOE 4 negative);
- Disease Severity via MMSE at Screening (24-26, 27-30)
- PET/CSF status at Screening (PET+/CSF+, PET+/CSF-, PET+/CSF Unknown, PET-/CSF+)
- CSF evaluation at Screening (CSF evaluated, CSF not evaluated)
- AD Treatment at Screening (use of AChEI or memantine, no use of AChEI or memantine)
- Vitamin E use at Screening (0-400 IU/day, >400 IU/day)

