### 8.2.11.1.2 Power Calculations

Power calculations for the change-from-baseline treatment difference at 30 months (Week 130) were performed (via simulation) for CDR-SB even though there are no formal hypotheses for the endpoint in the long term trial. As shown in Table 9 the hypothesis is underpowered at Week 130, both marginally and when applying an informal sequential testing approach. Specifically, it is possible that formal statistical significance may be observed in the initial 104 week trial (under the prespecified multiplicity approach), while nominal marginal significance (ie, p-value < 0.02495) fails to be observed at Week 130, even if the true underlying effect of MK-8931 continues to increase. This is due to the assumed increased variance and dropout rate over time, with 90% of subjects who complete the base study assumed to continue on into the extension.

Table 9 Power Calculations (MK-8931 40 mg / MK-8931 40 mg vs. Placebo / MK-8931 40 mg)

Marginal Probability †	(%)
CDR-SB at Week 130	73.9
Sequential Probability	
Success ‡ for CDR-SB at Week 104 and CDR-SB at Week 130	73.4
Conditional Probability	
Success ‡ for CDR-SB at Week 130 given success on CDR-SB at Week 104	76.1
† Marginal power calculations at Week 130 do not require success at Week 104. ‡ 40 mg dose only Calculations are based on N=1350 randomized (450 subjects/arm) incorporating the assumed dropout rate of 25% at Week 104 and 37% at Week 130 ( $\alpha = 0.02495$ ).	

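### Section 8.2.12 sets out to assess consistency of the treatment effect across 11 factors but plans no estimate of how the effect differs between levels

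*Combined protocol and SAP*

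**What the plan says.** Section 8.2.12 applies to CDR-SB, CCS-3D and ADCS-ADL MCI at Week 130. Its purpose and method come in one sentence: "The consistency of treatment effect across various subgroups will be assessed through the computation of within group summary statistics". These summaries carry nominal 95% CIs. The section then says "model-based between-group treatment differences (or hazard ratios, as appropriate) and the corresponding 95% CIs will be constructed for those comparisons" of active/active with placebo/active, but only where both arms have at least 75 subjects in that level. The groups compared there are treatment arms inside one level, not levels of a factor.

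Eleven factors follow: eight with two levels, and three (race, region, PET/CSF status) with four. On interactions the section says: "No formal statistical testing of the treatment by subgroup interactions will be performed". It mentions no interaction estimate or interval, and no rule for calling a factor consistent or inconsistent.

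Two other sections bear on this. Section 8.2.10 says that the long-term trial has no formal hypotheses. Section 8.2.11.1.2 says of the overall CDR-SB comparison that "the hypothesis is underpowered at Week 130".

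**The concern.** Consistency is a statement about how much the treatment effect differs from one level to another. The planned output gives the effect level by level and leaves that comparison to the reader. A common shortcut is to note which intervals exclude zero and which do not. That shortcut compares two levels of precision as much as two effects. It works worst when each level has moderate power, which is the situation when a comparison with 73.9% power overall is cut in two. At stake is a descriptive claim that the drug works in one level and not in another, made from data that fit a uniform effect, with nothing in the table to show how imprecise the contrast is.

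**Working it through.** **Inputs.** Table 9: marginal power 73.9% at Week 130 for 40/40 versus placebo/40, α = 0.02495, 450 randomised per arm, 37% loss by Week 130. Table 8: 30-month SD 3.05, correlation with baseline 0.359, 30-month mean change 2.13. Section 8.2.12: 95% intervals per level.

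**Step 1. The plan's own figure.** The 73.9% came from simulation and Section 8.2.11 gives no assumed treatment effect, so it cannot be recomputed forwards. It can be inverted. Taking α as two-sided (an assumption; sidedness is not stated):

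effect/SE = z(1 − 0.02495/2) + z(0.739) = 2.242 + 0.640 = 2.882.

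For scale, the baseline-adjusted SD is 3.05 × √(1 − 0.359²) = 2.847 and n per arm is 450 × 0.63 = 283.5. Then SE = 2.847 × √(2/283.5) = 0.239, and the implied effect is 2.882 × 0.239 = 0.69 points, or 32% of 2.13. Varying the SD, the effective n (283.5 to 450) and sidedness moves the implied effect between 0.49 and 0.74 points. Step 2 needs only the ratio 2.882.

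**Step 2. Identical effects, two levels.** A level holding share s of the information has ratio r = 2.882 × √s. Its 95% CI excludes zero with probability p = Φ(r − 1.96) + Φ(−r − 1.96). The levels contain different subjects, so exactly one interval excludes zero with probability p₁(1 − p₂) + p₂(1 − p₁).

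| Split | r₁, r₂ | p₁, p₂ | Disagree |
|---|---|---|---|
| 50/50 | 2.04, 2.04 | 0.531, 0.531 | 2 × 0.531 × 0.469 = 0.498 |
| 70/30 | 2.41, 1.58 | 0.674, 0.352 | 0.674 × 0.648 + 0.352 × 0.326 = 0.552 |

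A simulation of 1,000,000 draws at 50/50 gave 0.499.

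**Step 3. How far this depends on the assumptions (50/50).**

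- One-sided α in Step 1: 49.5%.
- Half the implied effect: 28.9%.
- No effect: 2 × 0.05 × 0.95 = 9.5%.
- Other reading rules at the implied effect: the two 95% CIs fail to overlap in 0.6% of cases, and the two estimates have opposite signs in 4.1%.

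**Step 4. What a between-level estimate would show.** The SE of the difference in effects is SE × √(1/s + 1/(1 − s)).

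- At 50/50 this is 2 × SE. The 95% half-width is 1.96 × 2/2.882 = 1.36 times the assumed effect, or 1.96 × 2 × 0.239 = 0.94 CDR-SB points.
- At 80/20 it is 2.5 × SE. The half-width is 1.96 × 2.5/2.882 = 1.70 times the effect, or 1.17 points.
- With identical effects this interval excludes zero 5% of the time, whatever the size of the common effect (5.0% in simulation).
- If the levels truly differed by the whole assumed effect, the ratio at 50/50 would be 2.882/2 = 1.44, and the interval would exclude zero with probability Φ(1.44 − 1.96) = 0.30.

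**The case against.** The strongest reply is that the analysis is openly descriptive. There are no formal hypotheses, the subgroup intervals are labelled nominal, interaction testing is expressly declined, and nothing in the documents turns on subgroup consistency. A reader can also recover an approximate between-level contrast by subtracting two per-level estimates and combining their half-widths by root-sum-square. All of this stands, and it limits the consequence. It does not explain the omission: declining a p-value is one choice, and leaving out the estimate that matches the stated purpose is another.

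A second reply is that the remedy is weak, since Step 4 gives it only about a 30% chance of detecting a difference as large as the whole effect. That is correct. A wide interval must therefore not be read as evidence of consistency, and the wording has to say so.

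A reader might infer three stronger points that the documents do not support.

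- That the plan would itself label identical effects inconsistent half the time for every factor. Section 8.2.12 contains no such rule, and Table 9 covers one endpoint and one contrast.
- That misleading patterns are close to certain over all the factors. No subgroup splits or correlations between factors are given. The 75-per-arm rule will remove some levels, and the PET-negative/CSF-positive level is empty in the FAS, which Section 8.2.4.1 restricts to PET-positive subjects.
- That the 75-subject minimum is defective because it does not count observed Week 130 scores. Section 8.2.7.1 uses all available initial-trial data in the longitudinal model, so that restriction is debatable. The percentage beside the 75 is stated as approximate and changes no result.

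**Conclusion.** The gap is real and modest. Section 8.2.12 names consistency of effect as its aim and plans no estimate of the difference in effect between levels for any of the 11 factors. The size of the problem can be stated only conditionally. It is about 50% disagreement under identical effects for an evenly split two-level factor, and 55% at 70/30. This applies to CDR-SB in the 40/40 versus placebo/40 comparison, at the effect implied by 73.9% power, and only if levels are compared by whether each interval excludes zero. It falls to about 10% if there is no effect. The calculation also assumes a normal approximation, information proportional to subgroup share, and both levels passing the 75-per-arm rule. The documents give no power for 12/12 versus placebo/40, CCS-3D or ADCS-ADL MCI, so no figure can be given for those. In a trial without formal hypotheses this is a cheap improvement to the plan and does not undermine its primary analysis.

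**What to change.** For each factor whose levels meet the 75-per-arm rule, and for each of the three endpoints, fit one model on the FAS: the Section 8.2.7.1 model with treatment-by-time-by-subgroup terms and the lower-order terms they need. Report the between-level difference in the Week 130 treatment effect with a nominal 95% CI and no p-value. For a factor with more than two eligible levels, give each difference against a named reference level. Add to Section 8.2.12 that consistency is read from this estimate and not from whether separate intervals include zero, and that an interval including zero does not establish consistency. The statement declining formal interaction tests can stay.

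The cost is SAP wording, extra model terms and one more column in each subgroup display, with no new data. The downside is that the intervals will be wide (Step 4) and will often be inconclusive. Showing that imprecision is part of the purpose.

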### **8.2.13 Interim Analyses**

The independent eDMC will routinely evaluate unblinded safety analyses of all trial subjects while the initial 104-week trial is blinded. Additional safety analyses may be conducted throughout the trial as requested by the eDMC. The sponsor will be unblinded after completion of the initial 104-week trial.

### **8.2.14 Compliance/Medication Adherence**

In this study, as part of the routine recording of the amount of study treatment taken by each subject, the number of tablets remaining in study packaging will be counted, reviewed, and recorded at regular intervals. These results will be used to calculate subject compliance. A day within the study will be considered an “On-Therapy” day if the subject takes one tablet.

For a subject who is followed for the entire study period, the “Number of Days Should be on Therapy” is the total number of days from the subject’s first dose to the last scheduled day for treatment administration for that subject. For a subject who discontinued from the study permanently, the “Number of Days Should be on Therapy” is the total number of days from the subject’s first dose to the date of the last dose of study medication.

For each subject, percent compliance will then be calculated using the following formula:

$$\text{Percent Compliance} = \frac{\text{Number of Days on Therapy}}{\text{Number of Days Should be on Therapy}} \times 100.$$

Summary statistics will be provided on percent compliance by treatment group for the FAS population.

### **8.2.15 Extent of Exposure**

Basic summary statistics for the number of doses taken by timeframe (e.g., 0-3 months, 4-6 months) as well as overall, will be provided by treatment group. Cumulative measures of exposure (e.g., Took at least 1 dose, Took at least 30 doses) will also be provided by treatment group.

## **9.0 LABELING, PACKAGING, STORAGE AND RETURN OF CLINICAL SUPPLIES**

### **9.1 Investigational Product**

The investigator shall take responsibility for and shall take all steps to maintain appropriate records and ensure appropriate supply, storage, handling, distribution and usage of investigational product in accordance with the protocol and any applicable laws and regulations.

Clinical Supplies will be provided by the Sponsor as summarized in [Table 10](#).

Table 10 Product Descriptions

Product Name & Potency	Dosage Form
MK-8931 12 mg	tablet
MK-8931 40 mg	tablet

### **9.2 Packaging and Labeling Information**

Clinical supplies will be affixed with a clinical label in accordance with regulatory requirements.

Medication will be provided in bottles.

At the visits specified in the Trial Flow Chart (Section 6), the site will dispense medication using the IVRS/IWRS system. The site may provide a ‘calendar sleeve’ that wraps around itself and can slide up and down the bottle to expose the medication label as required. The pull off tab on the ‘calendar sleeve’ offers a visual reminder to help subjects/caregiver take their trial medication. The intention of the sleeves is to assist the subject/caregiver/trial partner to remember when the subject missed a dose. The sponsor will provide the sleeve to the sites and site personnel will slide them onto each bottle.

Additional instructions regarding the calendar sleeves will be provided to sites.

When the subject/caregiver/trial partner returns to the clinical site, a physical pill count will be utilized for drug accountability and recorded in the eCRF.

### **9.3 Clinical Supplies Disclosure**

The emergency unblinding call center will use the randomization schedule for the trial to unblind subjects and to unmask treatment identity. The emergency unblinding call center should only be used in cases of emergency (see Section 7.1.4.2). In the event that the emergency unblinding call center is not available for a given site in this trial, the central electronic randomization system (IVRS/IWRS) should be used in order to unblind subjects and to unmask treatment/vaccine identity. The Sponsor will not provide random code/disclosure envelopes or lists with the clinical supplies.

Treatment identification information is to be unmasked ONLY if necessary for the welfare of the subject. Every effort should be made not to unblind the subject unless necessary.

In the event that unblinding has occurred, the circumstances around the unblinding (e.g., date and reason) must be documented promptly, and the Sponsor Clinical Director notified as soon as possible. Once an emergency unblinding has taken place, the principal investigator, site personnel, and Sponsor personnel may be unblinded so that the appropriate follow-up medical care can be provided to the subject.

### **9.4 Storage and Handling Requirements**

Clinical supplies must be stored in a secure, limited-access location under the storage conditions specified on the label.

Receipt and dispensing of trial medication must be recorded by an authorized person at the trial site.

Clinical supplies may not be used for any purpose other than that stated in the protocol.

In order to align with regional standard medical practice, trial sites in Japan are allowed to dispense subjects' treatment kits between drug dispensing visits identified in the protocol. Study medication will continue to be dispensed using the Interactive Voice Response System; however, study sites may increase the frequency with which study medication is dispensed to study participants in order to follow institutional regulations and/or local standard of care. All trial sites using partial dispensing options must follow the Merck guidance provided in the "Procedure for Investigational Medicinal Product (IMP) Management" document.

### **9.5 Discard/Destruction>Returns and Reconciliation**

The investigator is responsible for keeping accurate records of the clinical supplies received from the Sponsor or designee, the amount dispensed to and returned by the subjects and the amount remaining at the conclusion of the trial. For all trial sites, the local country Sponsor personnel or designee will provide appropriate documentation that must be completed for drug accountability and return, or local discard and destruction if appropriate. Where local discard and destruction is appropriate, the investigator is responsible for ensuring that a local discard/destruction procedure is documented.

## **9.6 Standard Policies**

Trial site personnel will have access to a central electronic randomization system (IVRS/IWRS system) to allocate subjects, to assign drug to subjects and to manage the distribution of clinical supplies. Each person accessing the IVRS system must be assigned an individual unique PIN. They must use only their assigned PIN to access the system, and they must not share their assigned PIN with anyone.

## **10.0 ADMINISTRATIVE AND REGULATORY DETAILS**

### **10.1 Confidentiality**

#### **10.1.1 Confidentiality of Data**

By signing this protocol, the investigator affirms to the Sponsor that information furnished to the investigator by the Sponsor will be maintained in confidence, and such information will be divulged to the institutional review board, ethics review committee (IRB/ERC) or similar or expert committee; affiliated institution and employees, only under an appropriate understanding of confidentiality with such board or committee, affiliated institution and employees. Data generated by this trial will be considered confidential by the investigator, except to the extent that it is included in a publication as provided in the Publications section of this protocol.

#### **10.1.2 Confidentiality of Subject Records**

By signing this protocol, the investigator agrees that the Sponsor (or Sponsor representative), IRB/ERC, or regulatory authority representatives may consult and/or copy trial documents in order to verify worksheet/case report form data. By signing the consent form, the subject agrees to this process. If trial documents will be photocopied during the process of verifying worksheet/case report form information, the subject will be identified by unique code only; full names/initials will be masked prior to transmission to the Sponsor.

By signing this protocol, the investigator agrees to treat all subject data used and disclosed in connection with this trial in accordance with all applicable privacy laws, rules and regulations.

#### **10.1.3 Confidentiality of Investigator Information**

By signing this protocol, the investigator recognizes that certain personal identifying information with respect to the investigator, and all subinvestigators and trial site personnel, may be used and disclosed for trial management purposes, as part of a regulatory submissions, and as required by law. This information may include:

- name, address, telephone number and e-mail address;
- hospital or clinic address and telephone number;
- curriculum vitae or other summary of qualifications and credentials; and

- other professional documentation.

Consistent with the purposes described above, this information may be transmitted to the Sponsor, and subsidiaries, affiliates and agents of the Sponsor, in your country and other countries, including countries that do not have laws protecting such information. Additionally, the investigator's name and business contact information may be included when reporting certain serious adverse events to regulatory authorities or to other investigators. By signing this protocol, the investigator expressly consents to these uses and disclosures.

If this is a multicenter trial, in order to facilitate contact between investigators, the Sponsor may share an investigator's name and contact information with other participating investigators upon request.

#### **10.1.4 Confidentiality of IRB/IEC Information**

The Sponsor is required to record the name and address of each IRB/IEC member that reviews and approves this trial. The Sponsor is also required to document that each IRB/IEC meets regulatory and ICH GCP requirements by requesting and maintaining records of the names and qualifications of the IRB/IEC members and to make these records available for regulatory agency review upon request by those agencies.

#### **10.2 Compliance with Financial Disclosure Requirements**

Financial Disclosure requirements are outlined in the US Food and Drug Administration Regulations, Financial Disclosure by Clinical Investigators (21 CFR Part 54). It is the Sponsor's responsibility to determine, based on these regulations, whether a request for Financial Disclosure information is required. It is the investigator's/subinvestigator's responsibility to comply with any such request.

The investigator/subinvestigator(s) agree, if requested by the Sponsor in accordance with 21 CFR Part 54, to provide his/her financial interests in and/or arrangements with the Sponsor to allow for the submission of complete and accurate certification and disclosure statements. The investigator/subinvestigator(s) further agree to provide this information on a Certification/Disclosure Form, commonly known as a financial disclosure form, provided by the Sponsor or through a secure password-protected electronic portal provided by the Sponsor. The investigator/subinvestigator(s) also consent to the transmission of this information to the Sponsor in the United States for these purposes. This may involve the transmission of information to countries that do not have laws protecting personal data.

#### **10.3 Compliance with Law, Audit and Debarment**

By signing this protocol, the investigator agrees to conduct the trial in an efficient and diligent manner and in conformance with this protocol; generally accepted standards of Good Clinical Practice (e.g., International Conference on Harmonization of Technical Requirements for Registration of Pharmaceuticals for Human Use Good Clinical Practice: Consolidated Guideline and other generally accepted standards of good clinical practice); and

all applicable federal, state and local laws, rules and regulations relating to the conduct of the clinical trial.

The Code of Conduct, a collection of goals and considerations that govern the ethical and scientific conduct of clinical investigations sponsored by Merck, is provided in Section 12.1 - Merck Code of Conduct for Clinical Trials.

The investigator also agrees to allow monitoring, audits, IRB/ERC review and regulatory authority inspection of trial-related documents and procedures and provide for direct access to all trial-related source data and documents.

The investigator agrees not to seek reimbursement from subjects, their insurance providers or from government programs for procedures included as part of the trial reimbursed to the investigator by the Sponsor.

The investigator shall prepare and maintain complete and accurate trial documentation in compliance with Good Clinical Practice standards and applicable federal, state and local laws, rules and regulations; and, for each subject participating in the trial, provide all data, and, upon completion or termination of the clinical trial, submit any other reports to the Sponsor as required by this protocol or as otherwise required pursuant to any agreement with the Sponsor.

Trial documentation will be promptly and fully disclosed to the Sponsor by the investigator upon request and also shall be made available at the trial site upon request for inspection, copying, review and audit at reasonable times by representatives of the Sponsor or any regulatory authorities. The investigator agrees to promptly take any reasonable steps that are requested by the Sponsor as a result of an audit to cure deficiencies in the trial documentation and worksheets/case report forms.

The investigator must maintain copies of all documentation and records relating to the conduct of the trial in compliance with all applicable legal and regulatory requirements. This documentation includes, but is not limited to, the protocol, worksheets/case report forms, advertising for subject participation, adverse event reports, subject source data, correspondence with regulatory authorities and IRBs/ERCs, consent forms, investigator's curricula vitae, monitor visit logs, laboratory reference ranges, laboratory certification or quality control procedures and laboratory director curriculum vitae. By signing this protocol, the investigator agrees that documentation shall be retained until at least 2 years after the last approval of a marketing application in an ICH region or until there are no pending or contemplated marketing applications in an ICH region or until at least 2 years have elapsed since the formal discontinuation of clinical development of the investigational product. Because the clinical development and marketing application process is variable, it is anticipated that the retention period can be up to 15 years or longer after protocol database lock. The Sponsor will determine the minimum retention period and notify the investigator when documents may be destroyed. The sponsor also recognizes that documents may need to be retained for a longer period if required by local regulatory requirements. All trial documents shall be made available if required by relevant regulatory authorities. The

investigator must consult with and obtain written approval by the Sponsor prior to discarding trial and/or subject files.

ICH Good Clinical Practice guidelines recommend that the investigator inform the subject's primary physician about the subject's participation in the trial if the subject has a primary physician and if the subject agrees to the primary physician being informed.

The investigator will promptly inform the Sponsor of any regulatory authority inspection conducted for this trial.

Persons debarred from conducting or working on clinical trials by any court or regulatory authority will not be allowed to conduct or work on this Sponsor's trials. The investigator will immediately disclose in writing to the Sponsor if any person who is involved in conducting the trial is debarred or if any proceeding for debarment is pending or, to the best of the investigator's knowledge, threatened.

In the event the Sponsor prematurely terminates a particular trial site, the Sponsor will promptly notify that trial site's IRB/IEC.

According to European legislation, a Sponsor must designate an overall coordinating investigator for a multi-center trial (including multinational). When more than one trial site is open in an EU country, Merck, as the Sponsor, will designate, per country, a national principal coordinator (Protocol CI), responsible for coordinating the work of the principal investigators at the different trial sites in that Member State, according to national regulations. For a single-center trial, the Protocol CI is the principal investigator. In addition, the Sponsor must designate a principal or coordinating investigator to review the trial report that summarizes the trial results and confirm that, to the best of his/her knowledge, the report accurately describes the conduct and results of the trial [Clinical Study Report (CSR) CI]. The Sponsor may consider one or more factors in the selection of the individual to serve as the Protocol CI and or CSR CI (e.g., availability of the CI during the anticipated review process, thorough understanding of clinical trial methods, appropriate enrollment of subject cohort, timely achievement of trial milestones). The Protocol CI must be a participating trial investigator.

